## 3. PARTICIPANT SELECTION AND ENROLLMENT PROCEDURES

### 3.1 Participant Eligibility Checklist

Protocol Title:	Phase II Trial of Organ Preservation Program Using Short-Course Radiation and FOLFOXIRI for Rectal Cancer (SHORT-FOX)
Protocol Number:	IRB56027/COR0019
Protocol Version Number/Date:	
Principal Investigator:	[name], MS

#### Subject Information:

Subject Name/MRN:

Gender:  Male  Female

	Eligibility Criteria	Window/ Last Date to Enroll	Supporting Documentation	Tab Label	Met? Y/N or N/A
1	Pathologically (histologically or cytologically) proven diagnosis of adenocarcinoma of rectum requiring total mesorectal excision as deemed by multidisciplinary evaluation	Within 180 days  Bx: 180 days	Diagnosis:  Bx date:		
2	At least 18 years of age	N/A	Age:		

3	For women of childbearing potential or who are not postmenopausal (see Appendix B for Definition of Menopausal Status), a negative urine pregnancy test must be done. Also, women of childbearing potential and men must agree to use adequate contraception (hormonal or barrier method of birth control; abstinence) for the duration of study participation and for up to 4 weeks following the study. Should a woman become pregnant or suspect she is pregnant while participating in this study, she should inform her treating physician immediately.	Within 45 days of enrollment  Pregnancy Test: 45 days	Result of pregnancy test:  Pregnancy Test date:		
4	ECOG Performance Status of 0-2	Within 45 days of enrollment  ECOG: 45 days	ECOG:  ECOG date:		
5	Ability to understand and the willingness to personally sign the written IRB-approved informed consent document	N/A	ICF date:		
6	
Patients must have acceptable organ and marrow function as defined below:
 
 
• ANC <math>\geq</math>1,500/uL
 
• Hg <math>></math> 8.0 g/dL; if blood transfusion is performed for achieving adequate hemoglobin level, the level should stay above goal for at least 1 week after transfusion
 
• Platelets <math>\geq</math>100,000/uL
 
• Total bilirubin <math>\leq</math>1.5X normal institutional limits
 
• AST(SGOT) / ALT(SGPT) <math>\leq</math>3X upper limit of normal
 
• Creatinine <math><</math>1.5X upper limit of normal or CrCL <math>></math>50 by Cockcroft-Gault
 
 
Patients must have CEA:
 
 
• CEA
 
	
Within 45 days of enrollment  CBCD: 45 days  CMP: 45 days
 
CEA: 45 days
	
CBCD date:  ANC Hg PLT  CMP date:  Bilirubin AST ALT Creatinine  CEA date:  CEA
		

7	
Clinical stage >T2N0 or low T2N0 rectal cancer (AJCC, 8th ed.) including no metastases based on the following diagnostic workup:
 
 
General history and physical examination with DRE (if deemed appropriate by treating physician) within 45 days prior to enrollment
 
Sigmoidoscopy within 90 days prior to enrollment
 
The following imaging studies are required within 45 days prior to enrollment:           
 
a) CT chest/abdomen/pelvis
 
b) MRI Pelvis
 
 
 
	H&P: 45 days	TNM:		
		Scope: 90 days	H&P: date: Scope date:		

Ineligibility Criteria					
1	Prior pelvic RT or chemotherapy for rectal cancer	N/A			
2	Upper T2N0 rectal cancers eligible for sphincter-preservation surgery	N/A			
3	Use of other investigational agents	N/A			
4	Ongoing or active infections requiring systemic antibiotic treatment or uncontrolled intercurrent illness including but not limited to symptomatic congestive heart failure, unstable angina pectoris, cardiac arrhythmia, or psychiatric illness/social situations that would limit compliance with study requirements.	N/A			
5	Any concurrent malignancy other than non-melanoma skin cancer or carcinoma in situ of the cervix. Patients with any previous malignancy without evidence of disease for >3 years will be allowed to enter the trial.	N/A			
6	Known hypersensitivity to 5-FU compounds	N/A			

7	Pregnant and breastfeeding women are excluded. Women of child-bearing potential who are unwilling or unable to use an acceptable method of birth control to avoid pregnancy for the entire study period and for up to 4 weeks after the study are excluded. (This applies to women who have experienced menarche and have not undergone successful surgical sterilization or are not postmenopausal).	N/A			
8	Because patients with immune deficiency are at increased risk of lethal infections when treated with marrow-suppressive therapy, known HIV-positive patients with detectable viral loads and/or receiving combination anti-retroviral therapy are excluded from the study	N/A			
9	Primary unresectable rectal cancer (tumor invading adjacent organs and en bloc resection will not achieve negative margins)	N/A			

\*All subject files must include supporting documentation to confirm subject eligibility. The method of confirmation can include, but is not limited to, laboratory test results, radiology test results, subject self-report, and medical record review.

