## **4. TREATMENT PLAN**

### **4.1 Pretreatment Studies**

The following will be completed after enrollment and before treatment begins

- HRQOL
- ctDNA
- AE Evaluation

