### **4.2 Treatment Schedule**

Study treatment will start within 30 days of eligibility determination.

Treatment will comprise 6 daily fractions of RT at 5 Gy per fraction followed 2-4 weeks later by approximately 4 months of chemotherapy.

Patients will be assessed for the primary outcome approximately 8 weeks (+/- 4 weeks) following completion of chemotherapy. Those who are not eligible for organ preservation will proceed with TME. All others will undergo organ preservation and surveillance for local regrowth for 2 years on protocol.

Treatment will be administered on an outpatient basis. No investigational or commercial agents or therapies other than those described may be administered with the intent to treat the patient's malignancy.

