## 9. STUDY CALENDAR

Activity	Pre-study (to be performed within 45 days of enrollment unless otherwise specified)	RT	Chemo	Primary Outcome Assessment 8 (+/- 4) weeks after Chemo (Time 0)	Follow-up after Time 0 g		
					Every 3 months	Months 3, 6, 12, 18, 24	Months 6, 12, 18, 24
Pregnancy Test a	X						
Biopsy within 180 days of enrollment	X			X e	X e		
Clinical Exam with DRE b	X		X d	X	X		
Procto/Sigmoidoscopy within 90 days of enrollment	X		X d	X	X		
CT chest/abdomen/pelvis c	X		X d	X			X
MRI pelvis	X		X d	X		X	
Labs-CBCD, CMP, CEA	X		X i	X			X
ECOG	X						
HRQOL	X j			X			X f
PET/MRI or FDG-PET c	X			X			
AE evaluation	X j	X	X	X L	X f		
ctDNA	X j	X k		X		X h	

aNegative pregnancy test by urine, for women non-post-menopausal as defined in Appendix.

bDRE may be deferred for clinical reasons, as determined by treating physician.

cMRI abdomen can substitute for CT abdomen/pelvis per physician discretion; PET imaging is *optional*. PET/MRI is preferred.

dRestaging after 8 (+/-4) weeks of chemotherapy. Procto/sigmoidoscopy and CT CAP can be omitted per physician discretion.

eIf biopsy is needed to rule out residual or progressive tumor, per the discretion of the surgeon

fAfter TME, patients will leave surveillance schedule but continue to receive HRQOLs, and be assessed for treatment-related AEs

gFollow-up appointments and activities 2 weeks before and 2 weeks after each timepoint are permitted, and may be completed virtually.

hAmong only those managed with organ preservation

iCEA does not need to be collected; pre-study CBCD, CMP may suffice for cycle 1 Day 1 chemo labs

jActivities to be done after enrollment and before treatment begins

kctDNA will be collected following completion of RT

LAn additional AE evaluation may be scheduled up to 3 months after completion of chemotherapy if needed

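### The only required pregnancy test is dated from enrollment, so a negative result may be up to 75 days old at the first pelvic radiation fraction, with no required test in between

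*Combined protocol and SAP*

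**What the plan says.** **The exclusion.** Ineligibility item 7 in section 3.1 states: "Pregnant and breastfeeding women are excluded". Its window column is marked not applicable.

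**The test.** For women who are of childbearing potential or not postmenopausal, eligibility criterion 3 in section 3.1 says that "a negative urine pregnancy test must be done", with the window "Pregnancy Test: 45 days" counted to enrollment. The Study Calendar (section 9) marks the test once, in the column headed "Pre-study (to be performed within 45 days of enrollment unless otherwise specified". Nothing is marked under RT, Chemo, the primary outcome assessment or follow-up. The footnote to that row reads "Negative pregnancy test by urine, for women non-post-menopausal as defined in Appendix" and sets neither a further timing nor a repeat.

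**Between enrollment and treatment.** Section 4.1 opens with "The following will be completed after enrollment and before treatment begins" and lists the quality-of-life questionnaires, a ctDNA sample and an adverse event evaluation. Calendar footnote j marks the same three. A pregnancy test is not among them.

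**Start of treatment.** Section 4.2 says: "Study treatment will start within 30 days of eligibility determination". Radiation comes first: "Treatment will comprise 6 daily fractions of RT at 5 Gy per fraction followed 2-4 weeks later by approximately 4 months of chemotherapy".

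**Other safeguards.** Criterion 3 also asks women of childbearing potential and men to agree to contraception while they take part and for up to 4 weeks afterwards. It tells a woman who is, or thinks she may be, pregnant to inform her treating physician at once.

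**The concern.** The test supports an exclusion that protects against exposure, and the first exposure is the first radiation fraction. The window is tied to a different event, enrollment, and a second permitted delay follows before treatment. A site that follows the text exactly can give pelvic radiation on a result that is many weeks old without deviating from the protocol.

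What is at stake is patient and fetal safety. A conception after the screening test could go unrecognized until after radiation, or until chemotherapy has begun. The trial does expect such patients: enrollment is open from age 18, and section 7.1.5 lists infertility and early menopause among the late effects of radiation in women.

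**Working it through.** The documents state no figure for the age of the test at treatment, so there is none to reproduce. It has to be built from the permitted windows.

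**Inputs**
- Test to enrollment: up to 45 days (section 3.1, criterion 3; section 9).
- Eligibility determination to start of treatment: up to 30 days (section 4.2).
- End of radiation to chemotherapy: 2 to 4 weeks, that is 14 to 28 days (section 4.2).
- Days by which eligibility determination precedes enrollment, *g*: not stated. Assumed range 0 to 30.
- Elapsed days for the radiation course: not stated for six daily fractions. Assumed 5 to 7, depending on weekends.

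**Maximum age of the result at the first fraction**

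Maximum age = 45 + 30 − *g*

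| *g* (days) | Maximum age at first fraction (days) |
|---|---|
| 0 | 45 + 30 − 0 = 75 |
| 7 | 45 + 30 − 7 = 68 |
| 14 | 45 + 30 − 14 = 61 |
| 30 | 45 + 30 − 30 = 45 |

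**Maximum age at chemotherapy cycle 1, taking *g* = 0**
- Shortest assumed course and gap: 75 + 5 + 14 = 94 days.
- Longest assumed course and gap: 75 + 7 + 28 = 110 days.

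**Is there a later test?** Section 4.1, calendar footnote j and the calendar's RT, Chemo and follow-up columns were read together. None contains a pregnancy test. Even in the most favorable row of the table, where radiation starts on the day of enrollment, a 45-day-old result is permitted.

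**The case against.** The strongest reply is that the test is not the only control. Item 7 is a criterion in its own right, with no window: a woman who is pregnant at enrollment is ineligible whatever an earlier test showed. Criterion 3 adds the contraception agreement and the instruction to report a suspected pregnancy. The checklist accepts self-report and record review as evidence of eligibility, and section 4.1 requires an adverse event evaluation before treatment. Also, 45 days is the common window for performance status, laboratory tests, examination and imaging, and the windows do not contradict one another.

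Much of this stands, and it rules out several stronger readings that a reader might infer:
- **That a pregnant woman would meet every criterion.** She would fail item 7. The gap is that no required test would detect the pregnancy.
- **That 45 days pass with no contraception undertaking.** The documents do not define when study participation begins. Section 3.2 requires consent before any study-specific procedure, so if the test is done as one, the undertaking may already apply. The uncovered time could be anywhere from 0 to 45 days.
- **That a pregnancy would stop treatment and cost an evaluable response among the 37.** Section 4.4 lists reasons for which patients may discontinue and does not name pregnancy. That consequence is not in the documents.

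The reply does not close the gap. Agreement and self-report are not tests, self-report works only if the woman suspects a pregnancy, and an adverse event evaluation need not reveal one.

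**Conclusion.** The point holds as a gap in detection. The protocol permits the first pelvic fraction on a negative result up to 75 days old if eligibility is determined on the day of enrollment. If it is determined up to 30 days earlier, the maximum lies between 45 and 75 days. These are upper bounds derived from the permitted windows, not stated figures or expected delays. The 94 to 110 days at cycle 1 rest further on the assumed length of the radiation course.

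It would go too far to say that the protocol cannot keep pregnant women out. The test window alone does not verify the exclusion at the time of exposure, and the other safeguards are partial. Only women who are not postmenopausal under Appendix A are concerned, so the number is small, and the trial's statistical figures are untouched. The change is worth making because the potential harm is serious and the correction is cheap.

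**What to change.** Reconcile criterion 3 and ineligibility item 7 (section 3.1), sections 4.1 and 4.2, and the Study Calendar:
- Keep criterion 3 as an eligibility item, but measure the window of the existing urine test back from the start of radiation instead of from enrollment. The sponsor sets the interval.
- Require a negative result to be documented before the first fraction, and show this in section 4.1 and the calendar.
- State when eligibility counts as determined relative to enrollment, and how the checklist entry for criterion 3 is completed if the test date falls after enrollment, so that the criterion stays verifiable.
- In the same edit, correct the cross-reference in criterion 3, which sends the reader to Appendix B for menopausal status. The definition is in Appendix A.

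**Cost.** Wording in three places. No test is added as a rule, since the one already required is dated differently, although it would have to be redone if radiation slipped beyond the chosen interval. Some tests would be done later than now, and a positive result could surface after enrollment. A patient who then withdraws before treatment is replaced under section 12.4.1, so the planned 37 is preserved.

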### **3.2 Informed Consent Process**

All participants must be provided a consent form describing the study with sufficient information for participants to make an informed decision regarding their participation. Participants must sign the IRB approved informed consent prior to participation in any study specific procedure. The participant must receive a copy of the signed and dated consent document. The original signed copy of the consent document must be retained in the medical record or research file.

### **3.3 Randomization Procedures**

Not applicable.

### **3.4 Study Timeline**

#### **Primary Completion:**

The study will reach primary completion 60 months from the time the study opens to accrual.

#### **Study Completion:**

The study will reach study completion 84 months from the time the study opens to accrual.

## **4. TREATMENT PLAN**

### **4.1 Pretreatment Studies**

The following will be completed after enrollment and before treatment begins

- HRQOL
- ctDNA
- AE Evaluation

### **4.2 Treatment Schedule**

Study treatment will start within 30 days of eligibility determination.

Treatment will comprise 6 daily fractions of RT at 5 Gy per fraction followed 2-4 weeks later by approximately 4 months of chemotherapy.

Patients will be assessed for the primary outcome approximately 8 weeks (+/- 4 weeks) following completion of chemotherapy. Those who are not eligible for organ preservation will proceed with TME. All others will undergo organ preservation and surveillance for local regrowth for 2 years on protocol.

Treatment will be administered on an outpatient basis. No investigational or commercial agents or therapies other than those described may be administered with the intent to treat the patient's malignancy.

#### **4.2.1 Radiation Therapy**

##### **4.2.1.1 External Beam Equipment and General Techniques**

Linear accelerators with a minimum energy of 6-15 MV will be used. Patients will

undergo CT treatment planning scans with patient supine or prone on a belly board per physician discretion and be treated in the same position. We will account for organ motion in multiple ways to ensure optimal target coverage while minimizing the dose to surrounding tissues, including: 1) cone-beam CT scans obtained on the linear accelerator in some cases to further verify target positioning, or 2) kilovoltage images through the On-Board Imaging system taken prior to delivery of each treatment field to verify position.

#### **4.2.1.2 Radiation Volumes and Prescribed Dose**

The intent of pre-operative treatment is to include the tumor bed plus the nodal groups at risk. A pelvic field will be treated initially using IMRT or 3D conformal radiotherapy (5 Gy x 5 fractions) with an additional optional boost fraction (5 Gy x 1 fraction) delivered sequentially to gross disease (including primary tumor and involved nodes). Assuming an alpha/beta ratio for rectal adenocarcinoma of approximately 5, 30 Gy in 5 fractions has a biological equivalent dose of 60 Gy (conventional fractionation to 50.4 Gy in 28 fractions has a biological equivalent dose of 68.5 Gy). IMRT is recommended but not required.

Radiation simulation utilizing CT-based planning will be performed prior to RT. If possible, patients will be treated in the supine or prone position with a full bladder technique. IV contrast can be administered at physician's discretion to patients without contrast allergy or compromised kidney function.

**Gross tumor volume (GTV):** This includes the primary tumor and any nodes believed to be involved grossly by metastatic disease. Assessment of the primary tumor and nodal disease may be made on the basis of procto/sigmoidoscopy, CT, PET-CT, MRI, and/or EUS. The entire rectal circumference at the level of the tumor should be included as GTV.

**Clinical target volume 1 (CTV1):** Includes the GTV, entire mesorectum and presacral space, and internal iliac nodes. The superior border will be placed at L5/S1 or L4/L5. If the tumor is a clinical T4 with anterior extension into an adjacent organ (i.e. prostate, cervix, bladder, vagina), the CTV is recommended to include the external iliac nodal regions. For patients with tumors invading the anal sphincter, the CTV is recommended to include the bilateral inguinal nodes and external iliac nodes.

**Clinical target volume 2 (CTV2) –** Includes the GTV plus 1-2 cm margin with additional inclusion of the entire mesorectum and presacral space up to physician discretion.

**Planning target volume (PTV) –** CTV1 and CTV2 will be expanded by a margin of 0.5 – 1 cm to account for daily setup variation to generate PTV1 and PTV2.

PTV1 will be treated to 25 Gy at 5 Gy/fraction.

PTV2 will be treated to 30 Gy at 5 Gy/fraction.

The sixth fraction to PTV2 may be omitted at the treating physician's discretion due to patient anatomy and/or tumor location.

All treatment planning will be performed with computerized dosimetry using IMRT or 3D conformal radiotherapy. Plans will be normalized such that 95% of the planning target volume will receive the prescription dose. RT dose variation of +/- 12% to the GTV is acceptable.

#### **4.2.1.3. Radiation Dose Constraints**

- Small Bowel (contoured as bowel loops): 40 Gy Dmax, V30 < 5 cc, V33 < 1 cc
- Femoral head and neck (recommended): V15 < 50%; V20 < 35%
- Bladder: V25 < 50%

#### **4.2.2 Chemotherapy**

Patients will be treated with approximately 4 months of FOLFOXIRI following RT. Patients who have performance status or conditions that may preclude use of FOLFOXIRI or mFOLFIRINOX may be treated with FOLFOX or XELOX instead at the discretion of the treating physician.

**Modifications of dose and schedule are allowed as per clinical judgment of patient's treating medical oncologist.** If deemed appropriate by the patient's Stanford medical oncologist, the patient can receive chemotherapy treatment with their local oncologist.

##### **4.2.2.1 FOLFOXIRI**

- Oxaliplatin 85mg/m^2 IV Day 1, dose rate per institutional standard of care
- Leucovorin 400 mg/m^2 IV Day 1 (optional), dose rate per institutional standard of care
- Irinotecan 165mg/m^2 IV Day 1, dose rate per institutional standard of care
- 5-Fluorouracil 3200mg/m^2 IVI Day 1, over 48 hours
- 14-day cycle for 8 cycles
- If necessary to accommodate holidays, patient schedule or other justified circumstances, schedule may be modified by +/- 7 days

##### **4.2.2.2 mFOLFIRINOX**

- Oxaliplatin 85mg/m^2 IV Day 1, dose rate per institutional standard of care
- Leucovorin 400 mg/m^2 IV Day 1 (optional), dose rate per institutional standard of care
- Irinotecan 150mg/m^2 IV Day 1, dose rate per institutional standard of care
- 5-Fluorouracil 2400mg/m^2 IVI Day 1, over 46 hours
- 14-day cycle for 8 cycles
- If necessary to accommodate holidays, patient schedule or other justified circumstances, schedule may be modified by +/- 7 days

##### **4.2.2.3 FOLFOX**

- Oxaliplatin 85mg/m^2 IV Day 1, dose rate per institutional standard of care
- Leucovorin 400 mg/m^2 IV Day 1 (optional), dose rate per institutional standard of care
- 5-Fluorouracil 2400mg/m^2 continuous infusion over 46 hours +/- 5-Fluorouracil 400mg/m^2 IV bolus Day 1

- 14-day cycle for 8 cycles
- If necessary to accommodate holidays, patient schedule or other justified circumstances, schedule may be modified by +/- 7 days

#### **4.2.2.4 XELOX**

- Oxaliplatin 130 mg/m^2 IV Day 1, dose rate per institutional standard of care
- Capecitabine 1000mg/m^2 PO BID Days 1-14
- 21-day cycle for 6 cycles
- If necessary to accommodate holidays, patient schedule or other justified circumstances, schedule may be modified by +/- 7 days

#### **4.2.3 Restaging during chemotherapy**

Patients will have restaging with clinical exam and MRI pelvis after 8 (+/-4) weeks of chemotherapy. If there is radiological or clinical evidence of disease progression, patient will be treated according to treating physician's discretion. If a patient chooses to receive chemotherapy locally, they must return to Stanford for the clinical exam and other imaging procedures required for restaging.

#### **4.2.4 Assessment of primary endpoint**

Patients' responses to therapy will be evaluated clinically 8 (+/-4) weeks after completion of radiation and chemotherapy.

#### **4.2.5 Follow-Up Schedule (Time 0 = assessment of primary outcome)**

Patients who achieve cCR and are candidates for organ preservation per multidisciplinary review will undergo surveillance per protocol schedule. If tumor shows near complete response, patient may continue to be observed until the next evaluable timepoint.

Additional scans and/or other tests may be performed and will be based on the clinical judgment of the treating physician.

Patients who are not candidates for organ preservation will proceed with TME. These patients will not proceed with the organ preservation surveillance schedule and instead be followed for cancer-specific outcomes (disease-free survival, colostomy-free survival and overall survival) per standard of care as directed by the treating physician. They will be assessed for AEs and health-related quality of life per Study Calendar.

For patients who achieve cCR and are on surveillance schedule, if suspicion of local regrowth (non-resolving residual abnormality that appears to increase in size or appears more suspicious in appearance or palpation, or imaging characteristics concerning for progression), patient will undergo a biopsy or a transanal full-thickness excision (TAE) if deemed appropriate to confirm. If biopsy is positive, patients will be managed per standard of care as directed by the treating physician.

Patients who pursue treatment for disease progression while on study will continue to be followed for OS, but discontinue routine AE assessment and QOLs, and follow-up with their treating physicians per standard of care.

After 2 years, all patients who initiated treatment on the protocol will be off study and followed for survival only. In general, patients who opt for organ preservation are recommended to continue to undergo surveillance years 3-5 as per below:

Recommend surveillance off study during years 3-5:

- Every 3-6 months
  - Exam and sigmoidoscopy
- Every 6 months
  - MRI pelvis and CT chest every 6 months

Follow-up PET/CTs or PET/MRI (preferred) are optional at any follow-up point, as per treating physician.

